### **7.7.2. Progression-Free Survival (PFS), Time-to-Disease Progression (TTP), and Overall Survival (OS)**

Median time and 90% confidence interval for PFS, TTP, and OS will be summarized for all eligible, treated subjects by treatment arm using Kaplan-Meier estimates. If medians have not been reached, 2-year PFS, TTP and OS should be reported instead, with 90% confidence intervals, calculated using time-to-event methods.

PFS = time from randomization to documented disease progression or death.

TTP = time from randomization until progression of disease

OS = time from randomization until death.

Subjects who are lost to follow-up are censored at the time of last tumor assessment for TTP and PFS and at the time of the last known contact for OS. All other subjects are censored at the time of analysis.

In addition to the summary table, PFS and OS will be displayed by treatment arm using Kaplan-Meier survival curves.

As a sensitivity analysis, all of the above analyses described in Section 7.6.2 will be repeated for the as-randomized population (intent-to-treat analysis).

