1.5 Rationale and Study Design

We hypothesize more complete blockade of the ER-signaling pathway may be achieved with selective estrogen receptor downregulator fulvestrant (given at a high dose) than may be achieved with the steroidal AI exemestane, and that this will result in either comparable or greater effectiveness for the fulvestrant-everolimus combination than the exemestane-everolimus combination. This is supported by preclinical data demonstrating that fulvestrant is particularly effective when combined with agents targeting the PI3K-AKT-m-TOR pathway in tumors that have undergone long-term estrogen deprivation, as is the case for patients who have acquired resistance to AI therapy.⁵⁰

We therefore propose to study the efficacy of fulvestrant in combination with everolimus for the treatment of post-menopausal HR-positive metastatic breast cancer in women who have progressed after treatment with an aromatase inhibitor. The combination of a novel class of agents (mTOR inhibitors) and an established standard treatment for metastatic HR-positive breast cancer may potentially increase the clinical benefit by targeting multiple different biological pathways.

This is a randomized, double-blind, placebo controlled Phase II study. It is expected that 130 patients will be accrued at 25 centers within the US. Patients will be randomized (1:1) to receive everolimus or placebo after consideration of stratification factors of performance status (0 vs.1), measurable disease (with or without non-measurable) vs. non-measurable disease, and prior chemotherapy for metastatic disease vs. no prior chemotherapy.

Induction Phase:

Treatment during the Induction Phase includes:

Fulvestrant 500 mg IM (two-250 mg injections per dose) on day 1 & 15 of Cycle 1, then 500 mg IM (two-250 mg injections) on day 1 of all subsequent cycles (every 28 days) plus everolimus 10 mg (two- 5 mg tablets) PO daily

OR

Fulvestrant 500 mg IM (two-250 mg injections per dose) on day 1 & 15 of Cycle 1, then 500 mg IM (two-250 mg injections) on day 1 of all subsequent cycles (every 28 days) plus placebo two tablets PO daily

Patients will be evaluated for disease response every 12 weeks (every 3 treatment cycles), +/- 1 week, and treated until disease progression, unacceptable toxicity or for a total of up to 12 cycles.

Continuation Phase:

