9.1 Primary Efficacy Endpoint

The primary efficacy endpoint is progression-free survival (PFS). PFS is defined as the time from randomization to documented disease progression or death. Based on results from the CONFIRM trial, median PFS among patients with AI-resistant disease on fulvestrant alone is 5.4 months. AI resistant disease is defined as: patients who have either relapsed while receiving adjuvant therapy with an aromatase inhibitor (anastrozole, letrozole, or exemestane) or have progressive disease while receiving an aromatase inhibitor for metastatic disease. (Patients previously treated with two or more prior cycles of fulvestrant are not eligible. Patients who have received one prior cycle (day 1 and day 15) of fulvestrant within 28 days of randomization are eligible so long as they meet other eligibility criteria). Randomization will be 1:1, stratified for balancing purposes using ECOG performance status (0 vs. 1), presence of measurable disease (yes vs. no), and prior chemotherapy (yes vs. no).

We hypothesize that the addition of everolimus to fulvestrant will result in an improvement in median PFS to 9.2 months. A one-sided stratified logrank test with a type I error rate of 10% will be used to evaluate whether the addition of everolimus shows promising improvement in PFS relative to fulvestrant alone. To have 90% power to detect the hypothesized improvement, enrollment of approximately 120 eligible patients (60 per arm) and full information of 98 events (deaths or progressions) are required. Allowing up to 10 patients to be ineligible or to not start study treatment, approximately 130 patients will need to be enrolled. With accrual of approximately 130 patients in 12 months, the required 98 events are expected to occur approximately 12 months after accrual is completed. Other endpoints that will be evaluated include clinical benefit rate (proportion stable or responding for at least 6 months), objective response rate (CR+PR), time to progression (TTP; defined as the time from randomization until progression of the disease), and overall survival (OS; defined as the time from randomization until death or censored at the date of last follow-up).

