PFS will be evaluated using the stratified log-rank test described above, as will TTP and OS. Kaplan-Meier plots will be used to graphically portray these time-to-event endpoints. Clinical benefit rate and objective response rates will be compared between arms using Fisher's exact tests. 90% exact binomial confidence intervals on the rates will be provided.

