9.3 Analyses of Other Secondary Endpoints

Other endpoints that will be evaluated include overall survival, time to progression, and objective response rate. Overall survival will be characterized using Kaplan-Meier plots and other descriptive metrics. The objective response rate will be provided for each arm, with 90% exact binomial confidence intervals. Median time to progression will be estimated for each arm.

10 Adverse Event Reporting

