## **2. INTRODUCTION**

### **2.1. Objective of the Abbreviated Statistical Analysis Plan**

This abbreviated statistical analysis plan (SAP) describes the planned analysis of the safety and efficacy data from the study to be prepared for a publication based on an outline provided by sponsor (Appendix 1). A detailed description of the planned tables, figures and listings (TFLs) to be prepared for the publication is provided in the accompanying TFL template document.

The intent of this document is to provide guidance for the analysis of data related to safety and efficacy to describe any applicable statistical procedures. In general, the analyses come directly from the protocol, unless they have been modified by agreement between the Sponsor and Quality Data Services, Inc. (QDS). A limited amount of information concerning this study (e.g., objectives, study design, treatment schedule, variables and endpoints) is summarized to help the reader interpret the accompanying TFL templates. This abbreviated SAP includes details about the variables and endpoints considered for the publication. The SAP also includes clarifications for analysis population (changes from protocol specified definitions), additional endpoints and sensitivity analyses not specified in the protocol but required for the publication. Attached signatures indicate approval of the statistical analysis sections of the SAP, as well as accompanying TFL templates. These sections must be agreed upon prior to database lock. Any revisions to statistical analyses required for the publication will be document in SAP Amendment (s). Any revisions to planned TFLs which do not require revisions to SAP will be documented in a Note to SAP.

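### The SAP's text and output list omit the protocol's primary PFS analysis: the one-sided 10% stratified log-rank test at 98 events

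*SAP*

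**What the plan says.** **Protocol 9.1** sets the decision rule: "A one-sided stratified logrank test with a type I error rate of 10% will be used to evaluate" whether adding everolimus to fulvestrant shows a promising PFS gain. It asks for 90% power and full information at 98 events. Randomization is stratified by ECOG performance status, "presence of measurable disease (yes vs. no), and prior chemotherapy (yes vs. no"). The section closes by saying that "PFS will be evaluated using the stratified log-rank test described above, as will TTP and OS". It adds that "Clinical benefit rate and objective response rates will be compared between arms using" Fisher's exact tests.

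**Protocol 9.3** is descriptive: "Other endpoints that will be evaluated include overall survival, time to progression, and objective response rate", with plots, medians, rates and intervals.

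**SAP 3.1** keeps the comparative primary objective. **SAP 7.2** assigns the primary efficacy analysis to eligible, treated subjects but does not say what that analysis is. **SAP 7.7.2** supplies the content: "Median time and 90% confidence interval for PFS, TTP, and OS will be summarized for all eligible, treated subjects by treatment arm", using Kaplan-Meier estimates, with 2-year rates if medians are not reached, and curves for PFS and overall survival (OS). The intent-to-treat sensitivity analysis repeats these outputs, citing a Section 7.6.2 that does not exist. **SAP Appendix 1** agrees: Table 14 holds medians or 2-year rates with 90% intervals, and Figures 1 and 2 are PFS and OS by arm.

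**SAP 2.1** says that in general "the analyses come directly from the protocol, unless they have been modified by agreement" between the sponsor and the analysis contractor. **SAP 10** refers to a separate template document for the outputs.

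**The concern.** The log-rank test is the only prespecified criterion for calling the trial positive, and it is the basis of the sample size. The SAP text contains no log-rank test, significance level, sidedness, event count for the analysis, or hazard ratio. The opening of SAP Section 7 ties its analyses to the outputs listed in Appendix 1. A programmer who follows 7.7.2 and that list exactly would deliver two medians with intervals and two figures. A reader of those outputs could not tell whether the trial met its criterion, or how large the estimated treatment effect was.

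**Working it through.** **Inputs (all Protocol 9.1):** median PFS 5.4 months on control and 9.2 months hypothesized; one-sided 10% level; 90% power; 98 events; 60 eligible patients per arm; 12 months of accrual and about 12 more to reach the events.

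**1. Reproduce the 98 events.** With exponential PFS, HR = 5.4/9.2 = 0.587 and ln HR = −0.5328.
- Freedman: (1.2816 + 1.2816)² × [(1 + 0.587)/(1 − 0.587)]² = 6.570 × 14.76 = 97 events. Power at 98 events is 90.2%.
- Schoenfeld: 4 × 6.570/0.5328² = 92.6, so 93 events. SE(ln HR) at 98 events = 2/√98 = 0.2020, and power = Φ(0.5328/0.2020 − 1.2816) = 91.2%.
- A two-sided 10% test would need 121 (Schoenfeld) or 127 (Freedman) events.

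So 98 belongs to the one-sided 10% log-rank test. The timing also fits. Uniform accrual over 12 months plus 12 months of follow-up, without dropout, gives event probabilities of 0.891 and 0.733, and 60 × (0.891 + 0.733) = 97.4 expected events.

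**2. What the test decides.** It is positive when the observed HR is at or below exp(−1.2816 × 0.2020) = 0.772. A two-sided 90% interval for the HR excludes 1 only below exp(−1.6449 × 0.2020) = 0.717. An observed HR between 0.717 and 0.772 is therefore a positive trial whose 90% interval spans 1.

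**3. Set the documents side by side.**

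| Element | Protocol 9.1 | SAP 7.7.2, ITT repeat, Table 14, Figures 1–2 |
|---|---|---|
| Between-arm test of PFS | Stratified log-rank | Not stated |
| Level and sidedness | 10%, one-sided | Not stated |
| Events at analysis | 98 | Not stated |
| Between-arm effect estimate | Not planned | Not planned |
| Per-arm Kaplan-Meier | Plots | Medians or 2-year rates with 90% CI; curves |

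**4. Can the listed outputs stand in for the test?** First a hand check. Take 49 events per arm and intervals as narrow as an exponential model allows, so SE(ln median) = 1/√49 = 0.1429 in each arm. Non-overlap of two 90% intervals needs a difference of 1.6449 × 2 × 0.1429 = 0.470. Dividing by 0.2020 gives z = 2.326. That is a one-sided level of about 1%, with power Φ(0.5328/0.2020 − 2.326) = 62%. On this favourable basis the intervals overlap in (0.912 − 0.622)/0.912 = 32% of positive trials.

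Kaplan-Meier intervals, which the SAP plans, are wider. Simulation settings were 60 per arm, exponential PFS, uniform 12-month accrual, cut at the 98th event, and log-log 90% intervals. The log-rank was unstratified, because the documents give no prognostic effects for the strata. The test was positive in about 90.6% of trials. Among those positive trials the two intervals for the median overlapped in about 59–61% with exact progression times. With 12-week scans and the permitted ±1 week window the figure was about 60–63%.

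**The case against.** The strongest reply is that nothing has been removed. The SAP is abbreviated and written for a publication, and SAP 2.1 carries protocol analyses over unless they were changed by agreement. The same section says what the SAP adds or changes (population clarifications, extra endpoints, sensitivity analyses), and dropping the primary test is not on that list. Appendix 1 is not closed either: it records a listing added by email and an adverse-event table that exists only in the templates. A p-value may well sit in the template for Table 14 or Figure 1.

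This stands, and it limits the point. A reader might infer that the SAP replaced the test with per-arm medians, or that the trial has no primary test. The documents do not support either reading. What the reply does not do is put the test into the SAP. The carry-over clause is hedged, and a template shows layout; the level, strata and event count belong in the analysis text.

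Second, nobody proposes to judge efficacy by overlapping intervals. True. The overlap figure only shows that the listed outputs are no substitute for the test.

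Third, a reader might assume that every progression is dated at an exact multiple of 12 weeks. That gives overlap in about 85% of positive trials, and an experimental median no larger than control in about 9%. Those figures come from artificial ties. The documents allow ±1 week around each scan, and with that window the results return to about 60–63% and under 1%.

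Fourth, the strata might be called undefined. That goes too far. SAP 7.2 already classifies subjects for response by their measurable-disease stratum at randomization, and SAP 7.3.5 takes the factors from the registration system (IWR). The prior-chemotherapy factor is worded as "prior chemotherapy for metastatic disease vs. no prior chemotherapy" in Protocol 1.5 and SAP 4.1 but is unqualified in Protocol 9.1 and SAP 7.3.5. That needs one wording, no more.

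Finally, the secondary objectives are framed as descriptive, so leaving the secondary tests out of the SAP is a matter for clarification.

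**Conclusion.** The point holds as an omission from the SAP text and its output list. The protocol's primary test is in force but is not written into SAP 7.7.2, its intent-to-treat repeat, or Table 14 and Figures 1 and 2. No between-arm effect estimate is planned in either document. Outputs produced exactly as listed would not answer the comparative objective in SAP 3.1.

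The 98-event figure is sound: power is 90.2% (Freedman) to 91.2% (Schoenfeld), with a positive result at an observed HR of about 0.77 or lower. In about 60% of positive trials the per-arm 90% intervals for median PFS would overlap. That figure rests on exponential PFS at the design medians, 60 per arm, no dropout, and an unstratified test. Whether the template already carries the test could not be checked. If it does, the remaining defect is that the SAP text does not specify it.

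**What to change.** Before database lock, by SAP amendment:

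1. In SAP 7.7.2 and Table 14, state the one-sided 0.10 log-rank test for PFS at 98 events. Stratify it by the three randomization factors as recorded in the IWR, which agrees with SAP 7.2. Run it in eligible, treated subjects and repeat it in the intent-to-treat population.
2. As a free improvement, add a hazard ratio from a Cox model stratified by the same factors, with a confidence interval. A two-sided 80% interval matches the one-sided 10% test. If only a 90% interval is shown, note that it can span 1 when the test is positive.
3. Minor clarifications: use one wording for the prior-chemotherapy stratum in both documents; state whether the Protocol 9.1 tests for time to progression, OS, objective response and clinical benefit are kept alongside the descriptive summaries; correct the 7.6.2 cross-reference to 7.7.2.

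The cost is one paragraph for the primary test, a few table rows and a few lines of SAS. No new data are needed.

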## **7.8. Safety Analysis**

### **7.8.1. Adverse Events**

Adverse events (AEs) will be graded using CTC Version 4, coded using MedDRA dictionary version 16.0, and flagged as treatment emergent if start date of the adverse event is on or after Cycle 1 Day 1 dosing. For adverse events with partial start date (i.e., with only month and year are recorded), the following imputation rule will be applied: 15th of the month or first dose date, whichever comes later.

All AEs and treatment-related AEs will be summarized for all treated subjects by toxicity grade and by treatment arm.

AEs with relationship reported as 'Definite', 'probable' and 'possible' are considered study drug related. AEs with relationship reported 'not likely' and 'not related' are considered not study drug-related. AEs with missing relationship will be considered study drug related.

The following by subject data listings will be prepared: subjects with serious adverse events, subjects with Grade 5 adverse events, and subjects with second primary cancer.

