4.3 Patient Randomization

Patients must meet all of the eligibility requirements listed in Section 3 prior to randomization. Treatment must begin \leq 7 working days from randomization.

An eligibility checklist has been appended as *an example* to the protocol and a usable version is available in separate study materials provided to the site. A confirmation of eligibility assessment by the investigator/site will be performed during the randomization process.

Information regarding stratification factors (performance status, measurable disease and prior chemotherapy) must be available at the time of randomization.

Once it is determined that a patient meets all eligibility requirements, the patient will be randomized to the study by site personnel using an electronic interactive web registration (IWR) system. Full information regarding registration and randomization procedures and guidelines can be found in the SRM provided to your site. All correspondence regarding patient randomization must be kept in the study records.

5 Treatment Plan

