10.1 Collection of Safety Information

Adverse Event (AE) is defined as any new untoward medical occurrence or worsening of a pre-existing medical condition in a patient administered a medicinal product in a clinical investigation and which does not necessarily have a causal relationship with this treatment. An AE can therefore be any unfavorable and unintended sign (including an abnormal laboratory finding, for example), symptom, or disease temporally associated with the use of a product (investigational or marketed), whether or not considered related to the product (investigational or marketed). Abnormal laboratory values or test results constitute adverse events only if they induce clinical signs and symptoms, are considered clinically significant, or require therapy.

Following written consent to participate in the study, all serious AEs should be collected on a patient. The collection of non-serious AE information should begin at initiation of therapy.

All identified AEs must be recorded and described on the appropriate page of the Case Report Form (CRF). If known, the diagnosis of the underlying illness or disorder should be recorded, rather than individual symptoms. The following information should be documented for all AEs: date of onset and resolution, severity of the event; the investigator's opinion of the relationship to investigational product (see definitions below); treatment required for the AE; cause of the event (if known); and information regarding resolution/outcome.

Severity

CTCAE term (AE description) and grade: The descriptions and grading scales found in the revised NCI Common Terminology Criteria for Adverse Events (CTCAE) Version 4.0 will be utilized for AE reporting. A copy of the CTCAE Version 4.0 can be downloaded from the CTEP web site (<http://ctep.cancer.gov>).

All appropriate treatment areas should have access to a copy of the CTEP CTCAE Version 4.0 (see Appendix E).

Attribution

The following categories and definitions of causal relationship or attribution to study drug should be used to assess Adverse Events:

- **Definite:** There is a reasonable causal relationship between the study drug and the event. The event responds to withdrawal of study drug (dechallenge) and recurs with rechallenge, if clinically feasible.
- **Probable:** There is a reasonable causal relationship between the study drug and the event. The event responds to dechallenge. Rechallenge is not required.

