### 6.1. Adverse Events

Adverse Event (AE) is defined as any new untoward medical occurrence or worsening of a pre-existing medical condition in a subject administered a medicinal product in a clinical investigation and which does not necessarily have a causal relationship with this treatment. An AE can therefore be any unfavorable and unintended sign (including an abnormal laboratory finding, for example), symptom, or disease temporally associated with the use of a product (investigational or marketed), whether or not considered related to the product (investigational or marketed).

Treatment-emergent AEs: any adverse event starting on or after the first treatment dose.

AE Severity:

**CTCAE term (AE description) and grade:** The descriptions and grading scales found in the revised NCI Common Terminology Criteria for Adverse Events (CTCAE) Version 4.0 will be utilized for AE reporting. A copy of the CTCAE Version 4.0 can be downloaded from the CTEP web site (<http://ctep.cancer.gov>).

All appropriate treatment areas should have access to a copy of the CTEP CTCAE Version 4.0 (see Protocol Appendix E)

AE Attribution (Relationship)

The following categories and definitions of causal relationship or attribution to study drug should be used to assess Adverse Events:

- Definite: There is a reasonable causal relationship between the study drug and the event. The event responds to withdrawal of study drug (dechallenge) and recurs with rechallenge, if clinically feasible.
- Probable: There is a reasonable causal relationship between the study drug and the event. The event responds to dechallenge. Rechallenge is not required.
- Possible: There is a reasonable causal relationship between the study drug and the event. Dechallenge information is lacking or unclear.
- Unlikely: There is doubtful causal relationship between the study drug and the event.
- Unrelated: There is clearly not a causal relationship between the study drug and the event or there is a causal relationship between another drug, concurrent disease, or circumstances and the event.

Categories 'Definite', 'probable' and 'possible' are considered study drug related. Categories 'not likely' and 'not related' are considered not study drug-related.

The development of a new cancer is to be regarded as an AE. New cancers are those that are not the primary reason for administration of study treatment and have been identified after inclusion of the subject into the clinical study.

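### The partial-date rule for adverse events moves events recorded in a month before first dose onto the first-dose date, so they are always flagged treatment-emergent

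*SAP*

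**What the plan says.** SAP Section 7.8.1 sets both the flag and the imputation. An adverse event is "flagged as treatment emergent if start date of the adverse event is on or after Cycle 1 Day 1 dosing". The imputation is introduced by "For adverse events with partial start date (i.e., with only month and year are recorded), the following imputation rule will be applied", and the imputed date is the 15th of the month "or first dose date, whichever comes later". Nothing limits this to events recorded in the month of first dose.

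SAP Section 6.1 defines treatment-emergent events as "any adverse event starting on or after the first treatment dose".

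Protocol Section 10.1 governs which events can be in the data before dosing. For serious events: "Following written consent to participate in the study, all serious AEs should be collected on a patient". For the rest: "The collection of non-serious AE information should begin at initiation of therapy".

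On outputs, SAP Section 7.8.1 states: "All AEs and treatment-related AEs will be summarized for all treated subjects by toxicity grade and by treatment arm". It also plans by-subject listings of serious and grade 5 events. SAP Section 7.2 makes treated patients evaluable for toxicity from their first treatment onward. SAP Appendix 1 mentions one further adverse-event summary table, which is in the separate template document.

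**The concern.** Imputation should fill in what is unknown. When the recorded month lies wholly before the month of first dose, the missing day does not matter: the event began before treatment whatever the day was. The rule overrides that recorded information and gives the event a start date known to be false. The flag derived from that date then disagrees with the SAP's own definition of treatment-emergent.

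What is at stake is the correctness of the flag, and of any table that selects events by it or by a period starting at first dose. In such a table a screening event would appear as arising on treatment. No efficacy result or hypothesis test depends on this rule.

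**Working it through.** The documents state no figure that depends on this rule, so there is none to reproduce. The check applies the rule as written.

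**Inputs.** The flag and the imputation rule come from SAP Section 7.8.1 and the definition from SAP Section 6.1. Protocol Section 10.1 gives the start of collection. Protocol Section 7.1.1 allows screening assessments up to 4 weeks before randomization, and Protocol Section 4.3 allows up to 7 working days from randomization to treatment.

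**Step 1: the rule as a formula.**

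imputed date = max(15th of recorded month, first dose date)

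treatment-emergent = (imputed date ≥ first dose date)

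Since max(a, b) ≥ b for any a and b, the second line is always true. Every event with only month and year recorded is treatment-emergent by construction.

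**Step 2: enumeration.** The rule was run for all 730 first-dose dates from 1 June 2013 to 31 May 2015 (illustrative dates) against all 48 months of 2012 to 2015. That gives 730 × 48 = 35,040 combinations, and 0 of them were not treatment-emergent.

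**Step 3: examples, with the corrected rule alongside.** The corrected rule uses the maximum only when the recorded month and year match first dose, and otherwise uses the 15th of the recorded month.

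| Recorded onset | First dose | SAP date | SAP flag | Corrected date | Corrected flag |
|---|---|---|---|---|---|
| May 2014 | 10 June 2014 | 10 June | yes | 15 May | no |
| May 2014 | 20 June 2014 | 20 June | yes | 15 May | no |
| June 2014 | 10 June 2014 | 15 June | yes | 15 June | yes |
| June 2014 | 20 June 2014 | 20 June | yes | 20 June | yes |
| July 2014 | 20 June 2014 | 15 July | yes | 15 July | yes |

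Only the earlier-month rows change. Across all earlier-month cases enumerated, the share flagged treatment-emergent falls from 100% to 0%.

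**Step 4: how often a pre-dose day falls in an earlier calendar month.** This assumes that onset is spread evenly over the window before first dose. The window length is also an assumption; 39 days is 28 days of screening plus about 11 calendar days for 7 working days.

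| Pre-dose window | Earlier-month days / all pre-dose days | Share |
|---|---|---|
| 7 days | 672 / 5,110 | 13% |
| 14 days | 2,520 / 10,220 | 25% |
| 28 days | 9,744 / 20,440 | 48% |
| 39 days | 17,724 / 28,470 | 62% |

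Crossing a month boundary is therefore ordinary. What makes the case rare is the missing day and the restriction to serious events, and the documents give no rate for either.

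**Step 5: what one such event could do.** Protocol Section 9.2 assumes 65 treated patients per arm. In an output restricted to treatment-emergent events or to the period from first dose, one wrongly included patient moves that arm's rate by 1/65 = 1.5 percentage points. In an output of all events in treated patients, nothing moves.

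**The case against.** The strongest reply is that no output visible in the SAP is restricted by the flag. The planned tables cover all events and treatment-related events in treated patients, and serious events are listed, not counted. A serious event before dosing in a patient later treated meets that wording whatever start date it is given. This stands. A reader might infer that the rule inflates the counts of serious or related events; the documents as available do not show that.

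A reader might also infer that the rule makes such events drug-related when attribution is missing. It does not. The sentence in SAP Section 7.8.1 that treats a missing relationship as related carries no date condition, so it would apply equally to a complete pre-dose date, and correcting the date rule would not change it.

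The collection rules also leave few events to misdate. Non-serious events are collected only from the start of therapy, Protocol Section 7.1.2.1 likewise starts adverse-event assessment after the first dose, and Protocol Section 10.1 asks for an onset date for every event. This stands too, and it limits the size.

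Finally, the rule is the same in both arms of a blinded trial, and Protocol Section 9.2 describes the safety comparison as descriptive. No systematic bias between arms is claimed here.

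These points do not remove the error in the flag. The SAP specifies the flag and, in Section 7.2, counts toxicity from first treatment. If a table applies either, a false first-dose date brings a screening event into the on-treatment period. Whether the additional table in the templates does so cannot be checked.

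**Conclusion.** The point holds as a minor defect. That the rule misclassifies every event recorded in a month before first dose follows from its wording and needs no assumption. That the misclassification conflicts with SAP Section 6.1 is equally plain.

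The practical size is small. The events reached are essentially serious ones after consent and before first dose, in patients later treated, with the day missing and an earlier month recorded. It would be too broad to say that every pre-dose event with a missing day is wrongly handled. When the recorded month is that of first dose, the true order is unknown, and assigning the event to treatment is a reasonable conservative choice.

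The effect on reported results depends on whether any output uses the flag or an on-treatment period, which the available documents do not settle. The serious-event listing and the attribution of events with missing relationship stay as they are either way.

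**What to change.** Amend the imputation sentence in SAP Section 7.8.1 along these lines: if the recorded month and year equal those of first dose, impute the later of the 15th and the first dose date; otherwise impute the 15th of the recorded month. Events from an earlier month then stay pre-treatment, while same-month and later-month results do not change. The 15th is already the SAP's convention for a missing day in Section 7.4, so no new principle is introduced.

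The cost is one sentence and one line of code, with no loss of conservatism where onset is uncertain. SAP Section 2.1 requires the analysis sections to be agreed before database lock and records later changes in an amendment, so the change belongs there. At the same time, check whether any table in the templates selects events by the flag or by time from first dose.
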